1.0 SUMMARY

Background: There are currently no proven treatment options for Coronavirus Disease 2019 (COVID-19) caused by Severe Acute Respiratory Syndrome Coronavirus 2 (SARS-CoV-2). Human convalescent immune plasma infusion (CIP) is an option for treatment of COVID-19.

Clinical Experience: Passive antibody therapy for infections has been used since the late 1800s and prior to the development of antimicrobial therapy in the 1940s^{1,2}. There is some evidence that convalescent plasma can provide neutralizing antibodies to SARS-CoV-2³. Convalescent serum was used in the 2013 Ebola epidemic. A small non-randomized study in Sierra Leone revealed a significant increase in survival for patients treated with convalescent whole blood compared to those who received standard treatment⁴.

Primary Objective: Evaluate whether CIP can reduce progression of critical illness among patients hospitalized for COVID-19

Primary Endpoints:

1. Transfer to the intensive care unit (ICU)
2. 28 day mortality

Secondary Objectives:

1. Evaluate the safety of CIP.
2. Evaluate cellular and humoral responses before CIP treatment and at CIP treatment.
3. Evaluate the effect of CIP as compared to non-transfused immunologic control patients.

Secondary Endpoints:

- Cumulative incidence of serious adverse events during the study period: transfusion reaction (fever, rash), transfusion related acute lung injury (TRALI), transfusion associated circulatory overload (TACO), transfusion related infection
- Rates and duration of SARS-CoV-2 PCR positivity at days 0, 4, 7, 14 and 21.
- Serum or plasma antibody titer¹ to SARS-CoV-2: Day 0, 7, 14, and 28
- Cellular and humoral immune responses at days 0, 7, 14, and 28 days
- Supplemental oxygen free days
- Ventilator free days
- ICU free days
- Sequential organ failure assessment (SOFA) score at days 0, 1, 2, 17, 14, 21, 28
- Need for vasopressors
- Need for renal replacement therapy
- Need for extracorporeal membrane oxygenation (ECMO)
- Hospital length of stay (LOS)
- ICU LOS
- Grade 3 or 4 adverse events (AEs)

Study Design: This is a single arm phase II trial to assess efficacy and confirm safety of infusions of anti-SARS-CoV-2 convalescent plasma in hospitalized patients with acute respiratory symptoms, with or without confirmed interstitial COVID-19 pneumonia by chest Xray or CT. A total of 29 eligible subjects will be enrolled to receive anti-SARS-CoV-2 plasma. Outcomes will be compared to hospitalized controls

¹ Measured by an anti-SARS-CoV-2 ELISA and serum antibody titer to SARS-CoV-2.

with confirmed COVID-19 disease through retrospective chart review.

In addition, the following Immunologic Controls will be used to meet secondary objectives described above:

1. PBMCs with 5-10 million cryopreserved cells per specimen will be obtained from the prospective COVID 19 Biorepository (2 timepoints per patient t (60 specimens total) and assessed for cellular and humoral immune responses.
2. Serum or plasma 500 UI each from up to 50 patients in the Covid-19 Biorepository will be collected (2 timepoints from each patient) (100 total specimens) will be evaluated for antibody and cytokine responses.

Study Population:

Inclusion Criteria for Enrollment

1. Patients must be 18 years of age or older
2. Patients hospitalized with COVID-19 respiratory symptoms within 72 hours of admission to a "floor" bed (non-ICU bed) and confirmation via SARS-CoV-2 RT-PCR testing.
3. Patient and/or surrogate is willing and able to provide written informed consent and comply with all protocol requirements.
4. Patients with hematologic malignancies or solid tumors are eligible.
5. Patients with autoimmune disorders are eligible.
6. Patients with immunodeficiency and organ or stem cell transplant recipients are eligible.
7. Patients who have received or are receiving hydroxychloroquine or chloroquine are eligible (but will be taken off the drug)
8. Prior use of IVIG is allowed but the investigator should consider the potential for a hyper-coagulable state.

Exclusion Criteria

1. Patients requiring mechanical ventilation or >6 liters per minute nasal cannula oxygen
2. Patients on other anti-COVID-19 trials being treated with tocilizumab (anti-IL-6 receptor), Siltuximab (anti-IL-2), Remdesivir, or other pharmacological trials that may be initiated hereafter.
3. A pre-existing condition or use of a medication that, in the opinion of the site investigator, may place the individual at a substantially increased risk due to study participation
4. Contraindication to transfusion or history of prior reactions to transfusion blood products.
5. Medical conditions for which receipt of 500-600 mL of intravenous fluid may be dangerous to the subject (e.g., decompensated congestive heart failure).

Clinical Controls (obtained via chart review):

1. Admitted to a "floor" bed (non-ICU bed) at UVAMC on/after March 30, 2020 due to confirmed COVID-19 disease using SARS-CoV-2 RT-PCR Testing
2. Age \geq 18 years of age
3. No receipt of convalescent plasma

Immunologic Controls:

1. PBMCs with 5-10 million cryopreserved cells per specimen present in the prospective COVID 19 Biorepository
2. Serum or plasma 500 UI each from up to 50 patients present in the COVID-19 Biorepository

Assessment and Data Acquisition:

1. Baseline: Age, sex, comorbidities, date of symptom onset, known COVID-19 contact, type of admission to the floor or ICU, APACHE score (ICU scoring system to classify disease severity and mortality risk), SOFA score (mortality prediction score based on organ function), clinical status, vital signs including temperature, respiratory rate, oxygen saturation, oxygen requirement, neutrophil count, lymphocyte count, CRP, chest x-ray, chest CT, location in hospital.
2. Safety and efficacy: Day 0 (baseline), 1, 2, 3, 4, 7, 14, 21, and 28 and once at day 60.
3. SARS-CoV-2 PCR from OP or NP swabs: Day 0, 4, 7, 14 and at any time when there is clinical suspicion for COVID-19.
4. Outcome measures: increased O₂ requirement (PaO₂/FiO₂ ratio or SpO₂/FIo₂), supplemental oxygen strategy (nasal cannula, high flow nasal cannula, noninvasive ventilation, intubation and invasive mechanical ventilation, rescue ventilation i.e. neuromuscular blocking agents, prone positioning, corticosteroids, ECMO), vasopressors, renal support, ICU LOS, ICU mortality, hospital LOS, hospital mortality, 28 day mortality.
5. Serum or plasma antibody titer² to SARS-CoV-2: Day 0, 7, 14, and 28. Samples from the COVID-19 Biorepository from non-transfused patients will be assayed at two similar timepoints as Immunologic Controls.
6. Blood for immune evaluations of cellular and humoral immunity before CIP infusion (day 0) and 7, 14 and 28 days after CIP infusion. Immune testing may be done at any time if the PI determines there is a need to evaluate acute immune responses (cytokines/chemokines levels). Samples from the Prospective COVID-19 Biorepository from non-transfused patients will be assayed at two similar timepoints as Immunologic Controls.
7. "Clinical controls" will have all relevant datapoints collected via chart review (i.e. biospecimens will not be collected prospectively)

Drug: Pathogen reduced SARS-CoV-2 convalescent plasma (1-2 units; 2 units are preferable but a single unit is allowable in the setting of safety/time/resource/etc concerns; ~200 mL each for a total of upto ~400 mls) given preferably in one day, but allowable to be given over 2 days if clinical circumstances delay infusions in 1 day), with titer to be determined after the unit has been infused.

Directed Donor Plasma Units: Healthy donors who have recovered from COVID-19 infection 21 days after symptom resolution will undergo a donor eligibility questionnaire. If eligible, blood will be drawn for ABO typing, HLA antibodies, and infectious disease panel screening. One additional red top tube will draw and sent to the [name] laboratory at UVA to test for levels of IgG anti-COVID-19 spike protein. No OP or NP PCR testing will be performed at day 21 given that donation will occur at day 28 or after. If the donor is eligible and matched, they will be called back to donate plasma at the ARC on day 28 after symptom resolution or later. The ARC or other local facility will collect blood for ABO, HLA, and infectious disease panel screening obtained via Emergency Use Authorization.

Immune Evaluations: Immune evaluations will be performed to determine if infusions of immune plasma enhance the development of anti-COVID-19 immune responses: peripheral blood mononuclear cells (PBMC) will be cryopreserved for measurements of specific anti-COVID-19 IFN-γ ELISpots, single cell high-dimensional immunophenotyping by mass cytometry and RNA-Seq; specific serum IgG, IgM and IgA antibodies COVID-19 and levels of Th₁/Th₂ serum cytokines at the designated time points at 0, 14, and 28 days after CIP infusion.

i. List of Abbreviations

ADR Adverse Drug Reaction

² Measured by an anti-SARS-CoV-2 ELISA and serum antibody titer to SARS-CoV-2.

ADE	Antibody-mediated enhancement of infection
BP	Blood pressure
CIP	Convalescent Immune Plasma
CTCAE	Common Terminology Criteria for Adverse Events
DBP	Diastolic Blood Pressure
DLT	Dose limiting Toxicity
DSMB	Data and Safety Monitoring Board
ECG/EKG	Electrocardiogram
EUA	Emergency Use Authorization
FDA	Food and Drug Administration
GCP	Good Clinical Practice
HBV	Hepatitis B virus
HCV	Hepatitis C virus
HIV	Human immunodeficiency virus
HTLV	Human T-cell lymphotropic virus
IB	Investigator’s Brochure
ICF	Informed Consent (Informed Consent Form)
ICH	International Conference on Harmonization
ICU	Intensive Care Unit
IEs	Immune Evaluations

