2.3 Study Design

This is a single arm phase II trial to assess preliminary efficacy and confirm safety of infusions of anti-SARS-CoV-2 convalescent plasma in hospitalized patients with acute respiratory symptoms **with or without** confirmed interstitial COVID-19 pneumonia by CXR or chest CT. A total of 29 eligible subjects will be enrolled to receive high titer anti-SARS-CoV-2 plasma. Participants will be compared to a historical control group via retrospective chart review.

In addition, the following Immunologic Controls will be used to meet secondary objectives described above:

1. PBMCs with 5-10 million cryopreserved cells per specimen will be obtained from the prospective COVID 19 Biorepository (2 timepoints per patient t (60 specimens total) and assessed for cellular and humoral immune responses.
2. Serum or plasma 500 UI each from up to 50 patients in the Covid-19 Biorepository will be collected (2 timepoints from each patient) (100 total specimens) will be evaluated for antibody and cytokine responses.

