5.2.7 Enrollment, Screen Failures, and Study Completion

Patients are considered enrolled from time consented to participate until designated as a screen failure or have either been discontinued from the study or completed it. A screen failure is a patient who signed informed consent, but then was determined to be ineligible or withdraws from the study. Subjects are considered to have completed the study when they are followed through day 60 or have had an adverse event or death occurred prior to day 60.

Day -1 to 0 Baseline:

- A. Subject informed consent (obtained before performing study related activities)
- B. Baseline Evaluation at screening.
 1. Demographics (Age, sex ethnicity, race)
 2. Medical history (timing of exposure to COVID-19 source patient, acute and chronic medical condition, medications, allergies.) Any medical condition arising after consent should be recorded as AE.
 3. COVID-19 symptom screen (fevers, cough, shortness of breath, diarrhea, anosmia), onset of symptoms, source of contagion
 4. Vital signs

5. COVID-19 testing (RT-PCR) from nasopharyngeal, throat, tracheal aspirate or bronchoalveolar lavage and stool (optional) samples
6. Blood typing, CBC with differential, comprehensive metabolic panel
7. Serological testing: anti-SARS CoV-2 titers
8. Immune testing samples
9. Urine or serum pregnancy test for females of childbearing potential. Results from laboratory tests obtained up to 7 days before enrollment may be used for the pregnancy test.
10. Determination of eligibility as per inclusion/exclusion criteria, age, consent, positive for COVID-19, respiratory symptoms within 72 hours of admission

DAY 0 Baseline and Infusion:

1. Study Plasma Administration: 1-2 units of plasma will be transfused over 1-2 days. Time at start and end of infusion will be recorded and vital signs will be measured immediately prior to infusion, 10-20 minutes after start of infusion, at completion of infusion and 30-60 minutes after the end of the infusion
2. COVID-19 symptom screen (fevers, cough, shortness of breath)
3. Assessment of clinical status (8-point ordinal scale)
4. New medical conditions, concomitant medication, AE evaluation
5. Physical examination
6. COVID-19 testing (RT-PCR) from nasopharyngeal, throat or stool (optional) samples
7. Blood typing, CBC with differential, comprehensive metabolic panel, C-reactive protein
8. Serological testing: anti-SARS CoV-2 titers

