9. Blood for Immune evaluations of cellular and humoral immunity (4 green tops, 30-40 milliliters).

Day 1-7 (or for duration of hospitalization)

1. Vital signs daily (including supplemental oxygen requirements)
2. COVID-19 symptom screen (fevers, cough, shortness of breath)
3. Assessment of clinical status (8-point ordinal scale)
4. New medical conditions, AE evaluation
5. Physical examination
6. CBC with differential, comprehensive metabolic panel, CRP daily

Days 0, 4 (\pm 1 day), 7 (\pm 2 day), 14 (\pm 3 days), 21 (\pm 3 days), and 28 (\pm 3 days):

1. SARS-CoV-2 PCR from oropharyngeal or nasopharyngeal swabs: Day 0, 4, 7, 14, 21 and at any time when there is clinical suspicion for COVID-19.
2. Serum or plasma antibody titer to SARS-CoV-2: Day 0, 7, 14, and 28
3. Blood for immune evaluations of cellular and humoral immunity before CIP infusion (day 0) and 7, 14, and 28 days after CIP infusion (4 green tops, 30-40 milliliters). Immune testing may be done at any time if the PI determines there is a need to evaluate acute immune responses (cytokines/chemokines levels).

Key issues to consider follow up by phone, alive, at home, in hospital (ICU or not), on supplemental O₂ or not, back to work, fully and partially

- COVID-19 symptom screen (fevers, cough, shortness of breath)
- Assessment of clinical status (8-point ordinal scale)
- New medical conditions, AE evaluation

Day 60 (\pm 7 days):

1. COVID-19 symptom screen (fevers, cough, shortness of breath)

2. Assessment of clinical status (8-point ordinal scale)
3. New medical conditions, AE evaluation

One year (\pm 1 month) - *optional*

- 1. Serum or plasma antibody titer to SARS-CoV-2**
- 2. Blood for immune evaluations of cellular and humoral immunity**
- 3. CBC with differential, Comprehensive metabolic panel, PT/INR, PTT, Quantitative immunoglobulins**
- 4. Interval medical history**
- 5. Subject questionnaires regarding health status**

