7.0 STATISTICAL CONSIDERATIONS

7.1 Statistical Analyses

Twenty-nine evaluable patients will have 80% power to declare a significant decrease in ICU admissions from a historical control of 50% of hospitalized patients to 25% with a two-sided type I error of 0.05 (reject ICU admission rate=50% if only 8 or less patients are admitted to ICU among 29 evaluable patients). The historic control group will consist of 29 patients who are gender and age (within 5 years) matched.

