7.3 Endpoints

7.3.1 Primary Endpoints

- Transfer to ICU
- 28 day mortality

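### Controls' 28-day vital status comes only from charts while recipients are contacted to days 28 and 60, so control deaths after discharge may be missed

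*Combined protocol and SAP*

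**What the plan says.** Section 7.3.1 lists "28 day mortality" as a primary endpoint beside ICU transfer. The outcome list in section 1.0 names "ICU LOS, ICU mortality, hospital LOS, hospital mortality, 28 day mortality" as separate items, so the 28-day measure reads as going beyond death in hospital.

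For recipients, section 1.0 schedules "Safety and efficacy: Day 0 (baseline), 1, 2, 3, 4, 7, 14, 21, and 28 and once at day 60". Table I in section 6.0 also marks visits at days 28 and 60. Section 5.2.7 adds a contact list that begins "Key issues to consider follow up by phone, alive, at home, in hospital (ICU or not", and it treats a subject as having completed the study when "followed through day 60 or have had an adverse event or death occurred prior to day 60".

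For controls, section 2.3 states: "Participants will be compared to a historical control group via retrospective chart review". Section 7.1 adds: "The historic control group will consist of 29 patients who are gender and age (within 5 years) matched". Section 1.0 says the clinical controls "will have all relevant datapoints collected via chart review (i.e. biospecimens will not be collected prospectively". Neither these sections nor the control criteria in section 4.3 mention a phone call, a death registry or any other check on a control who has left hospital. None gives a rule for unknown status or defines day 0 for a control.

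Section 9.1 summarizes categorical endpoints by frequency and percentage. Its only efficacy test sets ICU admission against a fixed 50%.

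**The concern.** The two groups are observed differently on a primary endpoint. A recipient who goes home and dies on day 20 should be found at a scheduled contact. A control with the same course is found only if the death reached the hospital's chart. If the chart is silent and silence is read as survival, control mortality is too low and plasma looks worse than it is. Nothing in the reported percentages would reveal this. With few deaths expected among 29 controls, each missed death moves control mortality by 1/29 = 3.4 percentage points.

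**Working it through.** **The plan's own figure.** The only design calculation concerns ICU transfer, 50% against 25%, two-sided 0.05, 80% power. The one-sample normal approximation gives n = [(1.960 × 0.500 + 0.842 × 0.433) / 0.25]² = 28.92, so 29, and the stated figure reproduces. It contains no mortality rate, so the size of the present problem has to be built from assumptions.

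**Effect of unseen control deaths.** Let m be true control 28-day mortality, s the share of those deaths that occur after discharge, and u the share of those that are absent from the chart. None of the three is in the documents. If an unseen death is counted as survival:

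- understatement of control mortality = m × s × u
- expected missed deaths = 29 × m × s × u
- apparent plasma/control risk ratio with no true effect = 1 / (1 − s × u)

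| Assumed m, s, u | Understatement (points) | Missed deaths of 29 | Apparent risk ratio |
|---|---|---|---|
| 10%, 10%, 100% | 1.0 | 0.29 | 1.11 |
| 15%, 20%, 100% | 3.0 | 0.87 | 1.25 |
| 20%, 30%, 100% | 6.0 | 1.74 | 1.43 |
| 5%, 10%, 50% (wider range, low) | 0.25 | 0.07 | 1.05 |
| 30%, 30%, 100% (wider range, high) | 9.0 | 2.61 | 1.43 |
| any m, with s = 0 or u = 0 | 0 | 0 | 1.00 |

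At 10-20% mortality the true number of control deaths expected is 29 × 0.10 = 2.9 to 29 × 0.20 = 5.8.

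**Against sampling error.** The standard error of a 29 versus 29 difference is √(2m(1 − m)/29), which is 7.9, 9.4 and 10.5 points at m = 10%, 15% and 20%. The understatement is smaller than this in each matching row.

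**A mechanism in the other direction.** Section 5.2.6 removes recipients who exceed the oxygen limit or need ventilation before infusion. Section 4.3 applies the corresponding limits to controls only at admission. Recipients may enter up to 72 hours after admission. Suppose recipients must survive to infusion while controls count from admission, and let w be the share of deaths that fall in that window (assumed 5-30%). Recipient mortality is then understated by m − m(1 − w)/(1 − m × w):

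- m = 10%: 0.45 points (w = 5%) to 2.78 points (w = 30%)
- m = 20%: 0.81 points (w = 5%) to 5.11 points (w = 30%)

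This range overlaps the 1-6 points above, so the sign of the net error cannot be settled from the documents.

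**The case against.** The strongest reply is that the plan promises all relevant datapoints for controls and lists 28-day mortality among the outcomes. The parenthesis about biospecimens does not limit what is sought on vital status. Charts may hold later visits, readmissions or notices of death. No decision rule uses mortality, and the possible error is smaller than the noise. Recipient follow-up is also looser than it looks: the phone line is worded as issues to consider, section 5.3 allows withdrawal for loss to follow-up, and section 5.2.7 read literally lets any adverse event count as completion.

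Much of this stands. A reader might infer that control deaths are in fact missed and that the mortality comparison is therefore biased against plasma. The documents do not support that. They do not say that unknown status is counted as alive, the loss may be zero, and other features push towards plasma.

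The asymmetry itself is not answered. Promising datapoints is not the same as naming a source that can supply them after discharge. Sampling error shows in a confidence interval, whereas unequal ascertainment does not. A primary endpoint set beside matched controls will be read as a comparison even if no test is attached. An opposing bias is a second defect, not a correction of the first.

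**Conclusion.** The concern holds as a risk of unequal ascertainment. Followed as written, the plan seeks vital status by scheduled contact in one group and by chart alone in the other. Taken alone, this would bias the descriptive 28-day mortality comparison against plasma by 1-6 points, or 0.3-1.7 deaths among 29 controls. That size rests wholly on assumed values: 10-20% mortality, 10-30% of deaths after discharge, and none of those in the chart. It falls to zero if charts capture all later deaths. The net direction of the whole comparison is unknown. The ICU transfer test against a fixed 50% and the recipients' own mortality figures are not affected. This is a cheap improvement to make before the data are read, not a flaw that undermines the trial's decision rule.

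**What to change.** For the between-group mortality comparison, use one source and one cut-off in both groups: in-hospital death by day 28, taken from the chart and counted from a common day 0. Hospital mortality is already a listed outcome. Day 0 should be set so that controls, like recipients, must be alive and still within the entry limits on that day; otherwise the opposing bias remains. Report recipients' full 28- and 60-day mortality separately, without a control figure beside it.

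If 28-day vital status is kept for the comparison, ascertain it identically in both groups, name the source, and give best- and worst-case bounds for unknown status. With k unknown among 29, the bounds for that group lie k/29 apart.

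Do not censor controls at discharge or last contact. Patients discharged alive are probably at lower risk, so such censoring is informative. As a hypothetical, take 29 controls of whom 20 are discharged alive and censored before the first death, with 3 deaths among the remaining 9. The Kaplan-Meier estimate is 1 − 6/9 = 33%, against 3/29 = 10% if no discharged patient dies.

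The follow-up time for the primary endpoint, 28 days in section 7.2 and 6 months in section 9.2, should be reconciled in the same edit.

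The cost is analysis-plan wording and the same chart abstraction in both groups; the sample size stays at 29. The downside is that in-hospital death omits post-discharge deaths in both groups and depends on discharge timing, which may differ between recipients and historical controls.
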